9.3 Method of collection of safety information

Describe the method by which the safety information will be collected (e.g., with case report forms, at study visits, by telephone calls and with subjects).

Not applicable.

9.4 Frequency of data collection

Describe the frequency of data collection, including when safety data collection starts.

Not applicable.

9.5 Individuals reviewing the data

Identify the individuals who will review the data. The plan might include establishing a data and safety monitoring committee and a plan for reporting data monitoring committee findings to the IRB and the sponsor.

Not applicable.

9.6 Frequency of review of cumulative data

Describe the frequency or periodicity of review of cumulative data.

Not applicable.

9.7 Statistical tests

Describe the statistical tests for analyzing the safety data to determine whether harms are occurring.

Not applicable.

9.8 Suspension of research

Describe any conditions that trigger an immediate suspension of research.

Not applicable.

10.0 Risks

List the reasonably foreseeable risks, discomforts, hazards, or inconveniences to the subjects related to the subjects' participation in the research. Include as may be useful for the IRB's consideration, a description of the probability, magnitude, duration, and reversibility of the risks. Consider all types of risk including physical, psychological, social, legal, and economic risks. **Note: Loss of confidentiality is a potential risk when conducting human subject research and must be listed here.**

- If applicable, indicate which procedures may have risks to the subjects that are currently unforeseeable.
- If applicable, indicate which procedures may have risks to an embryo or fetus should the subject be or become pregnant.
- If applicable, describe risks to others who are not subjects.

Aims 1 and 2: Residents

It is believed our SABL is safe with minimum adverse effects based on existing research evidence. Our proposed lighting scheme follows the scientific consensus for persons with dementia and the recommendations of the American National Standards Institute and Illuminating Engineering Society. Ambient light schemes similar to the proposed SABL have also been evaluated in a few studies and did not report any negative effects. Additionally, the intensity and color of our SABL will be perceived similar to low-level daylight and does not cause any glare. Also, for lighting installation, [name] will work with the director of maintenance (DOM) at each facility to ensure the installation follows NH regulations. Altogether, evidence suggests that our SABL is safe with minimum adverse effects.

Potential but rare risks of exposure to the SABL may include increased agitation, skin rash, eye irritation, dizziness, and nausea. Another potential risk for participating in this study is loss of identifiable information. Because the smart lighting system will operate automatically, we anticipate the burden on supporting the operation of the intervention will be very minimal.

It is believed our SABL is safe, and we do not expect any risks occur caused by our proposed SABL based on current research evidence. The list of rare risks listed in this study was based on the adverse effect checklist used in other studies and we plan to monitor unexpected but possible risks to be extra cautious in this study despite that we do not expect any side effects.

A systematic review of 32 articles concludes that bright light interventions trend toward a positive impact and do not have significant adverse effects for persons with dementia (Mitolo et al., 2018). Currently, to our knowledge, only two prior studies reported adverse effects: one study reported deteriorated agitation and depression (Barrick et al., 2010; Hickman et al., 2007) and one study reported increased anxiety (Van Hoof et al., 2009). However, their light designs were very different from this proposed study, with much higher intensity (2000-3000 lux) (Barrick et al., 2010; Hickman et al., 2007), or much higher color temperature (CCT=17000K, very bluish) (Van Hoof et al., 2009). Our proposed lighting scheme follows the scientific consensus for persons with dementia (Figueiro et al., 2016), and the recommendations of the American National Standards Institute and Illuminating Engineering Society (Illuminating Engineering Society of North America, 2020). Moreover, the ambient light schemes and schedule similar to our proposed SABL, but without daylight incorporation, have also been evaluated in a few studies and did not report any negative effects (Figueiro et al., 2014; Figueiro et al., 2015; Figueiro et al., 2019; Figueiro et al., 2020). Additionally, the intensity and color of our SABL will be perceived similar to low-level daylight and does not cause any glare. Altogether, evidence suggests that our SABL is safe with minimum adverse effects.

Aim 3: Staff and administrators

The risks to participants are very minimal. There is a potential of increased burden for staff and administrators from completing the surveys and participating in the interviews. We anticipate the study procedures will not take more than 2 hours to complete. We will make every attempt to work around their schedule and will conduct the interview during times that work best for them, including evenings and weekends.

11.0 Potential Benefits to Subjects and Others

11.1 Potential Benefits to Subjects

Describe the potential benefits that individual subjects may experience from taking part in the research. If there is no direct benefit to subjects, indicate as such. Compensation is not considered a benefit. Compensation should be addressed in section 13.0.

Aims 1 and 2: Residents

There is no guarantee that residents will benefit from this research study. The possible benefits residents may experience include improvement with their mood, behaviors, and sleep due to the exposure to the SABL lighting intervention.

Aim 3: Staff and Administrators

Participants will not benefit from this research study.

11.2 Potential Benefits to Others

Describe the potential benefits to society or others.

The results of this research study may benefit other people in the future by helping us learn more about the use of lighting interventions in residents with dementia. The results may help further refine the lighting intervention to be more effective and practical to use for residents with dementia in nursing homes improved BPSD, sleep, quality of life, and health outcomes.

12.0 Sharing Results with Subjects

Describe whether results (study results or individual subject results, such as results of investigational diagnostic tests, genetic tests, or incidental findings) will be shared with subjects or others (e.g., the subject's primary care physicians) and if so, describe how information will be shared.

This study will not share individual participant results with the participating nursing homes, participants, staff caregivers, residents, and family. However, we can share the aggregate results of the study with the participating facilities, participants, or family, if they are interested.

13.0 Subject Payment and/or Travel Reimbursements

Describe the amount, type (cash, check, gift card, other) and timing of any subject payment or travel reimbursement. If there is **no** subject payment or travel reimbursement, indicate as not applicable.

Extra or Course Credit: Describe the amount of credit **and** the available alternatives. Alternatives should be equal in time and effort to the amount of course or extra credit offered. It is not acceptable to indicate that the amount of credit is to be determined or at the discretion of the instructor of the course.

Approved Subject Pool: Indicate which approved subject pool will be used; include in response below that course credit will be given and alternatives will be offered as per the approved subject pool procedures.

For resident, we will not provide any reimbursement.

For staff and administrators, we will provide an honorarium for individuals who help with resident assessment for aim 1 or intervention feasibility assessment for aim 3. For staff caregivers who provide information for one resident assessment, including assessment on agitation, other BPSD, affect, sleep, and intervention side effects, we will provide a gift card of \$15 for each assessment visits for each resident. For staffs and interviews to evaluate intervention feasibility, we will provide a gift card of \$15. There is no limit of the number of assessments that an individual staff member will help with. If an individual staff member earns more than \$300 over the course of one calendar year, the study team will need to pay the reimbursement by check. Use of small financial honoraria is reasonable to convey respect to staff caregivers' participation in the research in exchange for their time and associated workload burden and has been found to enhance participation.

14.0 Economic Burden to Subjects

14.1 Costs

Describe any costs that subjects may be responsible for because of participation in the research.

Participants will not have any research-related costs.

14.2 Compensation for research-related injury

If the research involves more than Minimal Risk to subjects, describe the available compensation in the event of research related injury.

If there is no sponsor agreement that addresses compensation for medical care for research subjects with a research-related injury, include the following text as written - DO NOT ALTER OR DELETE:

It is the policy of the institution to provide neither financial compensation nor free medical treatment for research-related injury. In the event of injury resulting from this research, medical treatment is available but will be provided at the usual charge. Costs for the treatment of research-related injuries will be charged to subjects or their insurance carriers.

For sponsored research studies with a research agreement with the sponsor that addresses compensation for medical care for research-related injuries, include the following text as written - DO NOT ALTER OR DELETE:

It is the policy of the institution to provide neither financial compensation nor free medical treatment for research-related injury. In the event of injury resulting from this research, medical treatment is available but will be provided at the usual charge. Such charges may be paid by the study sponsor as outlined in the research agreement and explained in the consent form.

It is the policy of the institution to provide neither financial compensation nor free medical treatment for research-related injury. In the event of injury resulting from this research, medical treatment is available but will be provided at the usual charge. Costs for the treatment of research-related injuries will be charged to subjects or their insurance carriers.

15.0 Resources Available

15.1 Facilities and locations

Identify and describe the facilities, sites, and locations where recruitment and study procedures will be performed.

If research will be conducted outside the United States, describe site-specific regulations or customs affecting the research, and describe the process for obtaining local ethical review. Also, describe the principal investigator's experience conducting research at these locations and familiarity with local culture.

The study will be conducted in nursing homes in local central Pennsylvania: 1) Christ the King Manor and 2) Centre Care. These two facilities have agreed to be the clinical sites for this study and the administrator has provided a letter of support. Additional nursing homes may be identified as needed. The PI has established research relationships with these two sites and other long-term care facilities in central PA.

15.2 Feasibility of recruiting the required number of subjects

Indicate the number of potential subjects to which the study team has access. Indicate the percentage of those potential subjects needed for recruitment.

Christ the King Manor has the capacity to house 160 residents and approximately 70% of residents are living with dementia.

Centre Care has the capacity to house 240 residents and approximately 65% of the residents have dementia.

15.3 PI Time devoted to conducting the research

Describe how the PI will ensure that a sufficient amount of time will be devoted to conducting and completing the research. Consider outside responsibilities as well as other on-going research for which the PI is responsible. Please only provide a response for the principal investigator – do **not** include information about any other study team members.

The PI [name] has secured at least 15% of her time and [name] has secured at least 8% of his time to be devoted to conducting and completing this research study.

15.4 Availability of medical or psychological resources

Describe the availability of medical or psychological resources that subjects might need as a result of their participation in the study.

Not applicable.

15.5 Process for informing Study Team

Describe the training plans to ensure members of the research team are informed about the protocol and their duties.

All research team members will be trained by the PI [name] and/or [name] prior to the start of the study. Additionally, PI [name] and [name] will conduct weekly meetings with the research team who are directly involved in data collection and study procedures and monthly meetings with all study team members.

16.0 Other Approvals

16.1 Other Approvals from External Entities

Describe any approvals that will be obtained prior to commencing the research (e.g., from engaged cooperating institutions IRBs who are also reviewing the research and other required review committees, community leaders, schools, research locations where research is to be conducted by the Penn State investigator, funding agencies, etc.).

The clinical facilities have provided a letter of support for conducting the study at the site.

16.2 Internal PSU Ancillary Reviews

DO NOT ALTER OR DELETE:

Ancillary reviews are reviewed by other compliance groups or individuals within Penn State that inform the IRB's review of a new study or a modification to an existing study.

PSU IRB may set applicable ancillary reviews for your study. Please refer to the HRP-309 Worksheet – Ancillary Review Matrix for more information (found in the CATS Library).

[Do not type here]

17.0 Multi-Site Study

If this is a multi-site study (i.e., a study in which two or more institutions coordinate, with each institution completing all research activities outlined in a specific protocol) and **the Penn State PI is the lead investigator**, describe the processes to ensure communication among sites in the sections below.

[Do not type here]

17.1 Other sites

List the name and location of all other participating sites. Provide the name, qualifications and contact information for the principal investigator at each site and indicate which IRB will be reviewing the study at each site.

Not applicable.

17.2 Communication Plans

Describe the plan for regular communication between the overall study director and the other sites to ensure that all sites have the most current version of the protocol, consent document, etc. Describe the process to ensure all modifications have been communicated to sites. Describe the process to ensure that all required approvals have been obtained at each site (including approval by the site's IRB of record). Describe the process for communication of problems with the research, interim results, and closure of the study.

Not applicable.

17.3 Data Submission and Security Plan

Describe the process and schedule for data submission and provide the data security plan for data collected from other sites. Describe the process to ensure all engaged participating sites will safeguard data as required by local information security policies.

Not applicable.

17.4 Subject Enrollment

Describe the procedures for coordination of subject enrollment and randomization for the overall project.

Not applicable.

17.5 Reporting of Adverse Events and New Information

Describe how adverse events and other information will be reported from the clinical sites to the overall study director. Provide the timeframe for this reporting.

Not applicable.

17.6 Audit and Monitoring Plans

Describe the process to ensure all local site investigators conduct the study appropriately. Describe any on-site auditing and monitoring plans for the study.

Not applicable.

18.0 Adverse Event Reporting

18.1 Adverse Event Definitions

For drug studies, incorporate the following definitions into the below responses, as written:	
Adverse event	Any untoward medical occurrence associated with the use of the drug in humans, whether or not considered drug related
Adverse reaction	Any adverse event caused by a drug
Suspected adverse reaction	
Any adverse event for which there is a reasonable possibility that the drug caused the adverse event. Suspected adverse reaction implies a lesser degree of certainty about causality than “adverse reaction”.
 
 • Reasonable possibility. For the purpose of IND safety reporting, “reasonable possibility” means there is evidence to suggest a causal relationship between the drug and the adverse event.
Serious adverse event or Serious suspected adverse reaction	
Serious adverse event or Serious suspected adverse reaction: An adverse event or suspected adverse reaction that in the view of either the investigator or sponsor, it results in any of the following outcomes: Death, a life-threatening adverse event, inpatient hospitalization or prolongation of existing hospitalization, a persistent or significant incapacity or substantial disruption of the ability to conduct normal life functions, or a congenital anomaly/birth defect. Important medical events that may not result in death, be life-threatening, or require hospitalization may be considered serious when, based upon appropriate medical judgment, they may jeopardize the patient or subject and may require medical or surgical intervention to prevent one of the outcomes listed in this definition.

Life-threatening adverse event or life-threatening suspected adverse reaction	An adverse event or suspected adverse reaction is considered “life-threatening” if, in the view of either the Investigator (i.e., the study site principal investigator) or Sponsor, its occurrence places the patient or research subject at immediate risk of death. It does not include an adverse event or suspected adverse reaction that had it occurred in a more severe form, might have caused death.
Unexpected adverse event or Unexpected suspected adverse reaction.	An adverse event or suspected adverse reaction is considered “unexpected” if it is not listed in the investigator brochure, general investigational plan, clinical protocol, or elsewhere in the current IND application; or is not listed at the specificity or severity that has been previously observed and/or specified.

For device studies, incorporate the following definitions into the below responses, as written:	
Unanticipated adverse device effect	Any serious adverse effect on health or safety or any life-threatening problem or death caused by, or associated with, a device, if that effect, problem, or death was not previously identified in nature, severity, or degree of incidence in the investigational plan or IDE application (including a supplementary plan or application), or any other unanticipated serious problem associated with a device that relates to the rights, safety, or welfare of subjects.

18.2 Recording of Adverse Events

Address the frequency and process for eliciting adverse event information from research subject, e.g., “Research subjects will be routinely questioned about adverse events at study visits.”

In the response, incorporate the following as written:

All adverse events (serious or non-serious) and abnormal test findings observed or reported to study team believed to be associated with the study drug(s) or device(s) will be followed until the event (or its sequelae) or the abnormal test finding resolves or stabilizes at a level acceptable to the investigator.

An abnormal test finding will be classified as an adverse event if one or more of the following criteria are met:

- The test finding is accompanied by clinical symptoms
- The test finding necessitates additional diagnostic evaluation(s) or medical/surgical intervention; including significant additional concomitant drug treatment or other therapy

NOTE: Simply repeating a test finding, in the absence of any of the other listed criteria, does not constitute an adverse event.

- The test finding leads to a change in study drug dosing or discontinuation of subject participation in the clinical research study
- The test finding is considered an adverse event by the investigator.

All adverse events (serious or non-serious) and abnormal test findings observed or reported to study team believed to be associated with the lighting intervention will be followed until the event (or its sequelae) or the abnormal test finding resolves or stabilizes at a level acceptable to the investigator. Research team members will visit the site biweekly during the 13 weeks of study period to monitor any adverse events.

An abnormal test finding will be classified as an adverse event if one or more of the following criteria are met:

- The test finding is accompanied by clinical symptoms. We will not be able to completely distinguish whether a clinical symptom is resulted from dementia or other comorbidities, or it is resulted from the SABL treatment. We will assess dementia-related symptoms, including behavioral and psychological symptoms at baseline and every other week throughout the 13-week study period. Also, during the 13-week study period, the SABL will only be provided for 4 weeks. When a clinical symptom occurs during those 4 weeks, we will compare the participant's symptoms with the baseline and non-intervention period to examine if the symptoms are possibly SABL-related. In addition, we will examine other comorbidities that may contribute to the clinical symptoms, such as delirium, urinary tract infection, and a new medical condition/procedure that may cause pain (e.g., tooth extraction, fall). We will collect all relevant information and document it and will observe if the same symptom occurs to other participants.
- The test finding necessitates additional diagnostic evaluation(s) or medical/surgical intervention; including significant additional concomitant drug treatment or other therapy.

NOTE: Simply repeating a test finding, in the absence of any of the other listed criteria, does not constitute an adverse event.

- The test finding leads to a change in study drug dosing or discontinuation of subject participation in the clinical research study

The test finding is considered an adverse event by the investigator.

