- 1) Data extraction from CMS Nursing Home Compare Website (<https://www.medicare.gov/care-compare/>): Data on facility characteristics, including number of certified beds, ownership, quality rating, participation in Medicaid, staffing, COVID-related data is publicly available and can be accessed through the link provided above.
- 2) Chart reviews: Data on resident characteristics, including age, race, sex, diagnoses, level of cognitive impairment, current medication use, current listed comorbidity and physical function, BPSD in the past two weeks, pain in the past two weeks, current vision status, current hearing status, and other clinical conditions.
- 3) Surveys based on staff caregivers' reports: The surveys will be conducted on paper and in-person with researcher administering the survey to the staff caregiver for proxy report of residents' dementia stage, agitation, other BPSD, affect, and side effects.
- 4) Personal light monitor, LYS button, placed on individual resident participants to measure lighting intensity (lux) and CS levels participants receive.

There will be seven visits for data collection throughout the 13-week of the study: baseline visit (week 1) and six follow-up visits, every other week (weeks 3, 5, 7, 9, 11, 13). The procedures for each visit are as follows:

Baseline visit: Procedures 1 through 4.

Follow-up visits: Procedures 3 and 4.

For the procedure 4, the light monitor will be worn 7 days a week during the data collection weeks (week 1, 3, 5, 7, 9, 11, & 13).

Aim 2: We will evaluate the fidelity of SABL delivery by measuring lighting intensity (lux) and CS levels.

Data collection procedures will include the following:

- 1) on-site manual light measurements
- 2) personal light monitor, LYS button, placed on individual resident participants (same as the procedure 4 in aim 1).

The procedures will be conducted primarily on site at the nursing home facilities.

The procedure 1 will be conducted twice a week throughout the 13-week study period.

For the procedure 2, as mentioned in aim 1, the light monitor will be worn 7 days a week during the data collection weeks (week 1, 3, 5, 7, 9, 11, & 13).

Aim 3: Staff and Administrators

Data collection methods include the following:

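### Other causes of a symptom are sought only in the SABL weeks, and no intercurrent-illness record is kept alike under SABL, control and washout

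*Protocol*

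**What the plan says.** Protocol section 18.2 accepts that a symptom cannot be fully separated from dementia or comorbidity. It notes that "during the 13-week study period, the SABL will only be provided for 4 weeks" and sets the trigger for a causality review: "When a clinical symptom occurs during those 4 weeks", the resident's symptoms are compared with baseline and with the period off the intervention. It goes on: "we will examine other comorbidities that may contribute to the clinical symptoms, such as delirium, urinary tract infection, and a new medical condition/procedure", giving tooth extraction and a fall as examples of the last. The findings are kept ("We will collect all relevant information and document it"), and the team "will observe if the same symptom occurs to other participants". No matching review is written for control or washout weeks.

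Section 7.2 places chart review (procedure 2) at the first visit only. Its content includes "current medication use, current listed comorbidity and physical function, BPSD in the past two weeks, pain in the past two weeks". The visit schedule reads "Baseline visit: Procedures 1 through 4" and then "Follow-up visits: Procedures 3 and 4", which are the staff survey and the light monitor. Table 2 agrees that resident characteristics are a baseline item.

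Section 19.1.2 runs an adverse-event checklist with nursing assistants every two weeks in all periods. It covers worsened behavioural symptoms, rash, eye irritation, dizziness and nausea, with an open category for other reactions. Section 18.3 has the investigator review every documented event. Where the cause is unresolved and the link to the device doubtful, the event counts as device-associated for reporting. The Aim 1 model (section 8.3 and the SAP) contains no illness variable.

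**The concern.** Side effects and agitation both sit in the first primary outcome (section 1.2). Infection, delirium, pain and falls are common-sense rival explanations for worsening behaviour in this population, and section 18.2 names them as such. Yet whether such a cause is looked for depends on both the exposure (a SABL week) and the outcome (a symptom has appeared). The reference weeks are left without the same information, although the protocol's own causality method relies on them. A symptom under SABL may be explained by an infection; a symptom under usual light stays in the reference level with its cause unrecorded. These data are also hard to recover reliably afterwards.

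**Working it through.** The documents give no side-effect or illness rate, so there is no planned figure to reproduce. The check is a comparison of the text, followed by two illustrations with assumed inputs.

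**Timeline.** From section 7.3, 1 + 4 + 2 + 4 + 2 = 13 weeks. SABL takes 4, leaving 13 − 4 = 9 weeks without a written other-cause review, 4 of them control weeks. Visits fall in weeks 1, 3, 5, 7, 9, 11 and 13. By these phase lengths each resident has 1 baseline visit, 2 in SABL weeks, 2 in control weeks and 2 in washout or post-period weeks.

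**What is collected, and when.**

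| Source | SABL weeks | Control and washout weeks | Names infection, delirium, pain or falls? |
|---|---|---|---|
| Chart review (7.2, procedure 2) | no | no | baseline only: pain, diagnoses, comorbidity |
| Staff survey and adverse-event checklist (7.2, 19.1.2) | yes | yes | no; open item only |
| Other-cause review (18.2) | yes, once a symptom appears | not written | yes |
| Removal for new illness (3.3.1) | possible | possible | only conditions meeting an exclusion criterion |

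Only the third row looks for these causes after baseline, and it is tied to SABL weeks.

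**Effect on the causality judgement.** A SABL-week symptom with an identified illness can be attributed to that illness. Illness in the reference weeks raises the level against which SABL-week symptoms are judged, without being recognised. Both lean towards attributing less to SABL. The section 18.3 default leans the other way, but it covers doubtful events and not those given an identified other cause.

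**The second check in 18.2.** All participants in a home receive SABL in the same weeks, while the other home is on usual light. A symptom seen in several residents of the SABL home is what a SABL effect would produce, and also what a home-wide infection would produce. The check cannot separate them.

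**How much goes unrecorded (illustration).** Assume the same 4-week illness rate r in both periods, with the 36 completers of section 8.2. Expected residents ill per 4-week period = 36 × r:
- r = 5%: 1.8
- r = 10%: 3.6
- r = 20%: 7.2

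The same number is expected under SABL and under control, but only those with symptoms in SABL weeks enter the written review. This counts missing information; it is not an estimate of bias.

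**CMAI (illustration).** Suppose illness affects a share f of one of the two homes during one block and adds δ points. The average SABL–control difference moves by f × δ / 2. With f = 0.25 and δ = 5 this is 0.625; with f = 0.50 and δ = 10 it is 2.5. If illness touches only one of the two visits in the block, these halve to about 0.3 and 1.25. Illness in a SABL block makes SABL look worse; illness in a control block makes it look better. For scale, d = 0.53 (section 8.2) is 0.53 × 10 = 5.3 to 0.53 × 15 = 7.95 points if the SD of differences is 10 to 15, which is also assumed.

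**The case against.** The best defence is that event collection is the same throughout: adverse effects are scheduled at all seven visits in both homes, site visits cover all 13 weeks, staff may report at any time, and the section 18.3 review has no time window. Whether the device caused an event is mainly a question for exposed weeks. The sentence on comorbidities does not itself repeat the 4-week limit, although it follows directly from one that sets it. All this stands, and it narrows the point to the extra other-cause review and the missing named items.

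Three stronger readings are tempting and should be resisted.

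- A reader might infer that the trial has no illness data. It has baseline diagnoses, comorbidity, medication and pain, documented findings from the SABL-week review, an open checklist item, and reasons for withdrawal (section 3.3.2).
- A reader might infer a bias of known size in SABL's favour. If a share q of episodes were set aside under SABL only, the SABL/control ratio with no true effect would be 1 − q, or 0.90 to 0.60 for q of 10% to 40%. But q is invented, no text says such episodes are set aside, and neither section 8.3 nor the SAP plans such a ratio.
- A reader might infer that the asymmetry is built into the CMAI estimate. CMAI, NPI-NH and ARS are collected alike in every period, and no rule removes or adjusts a score for illness. Confounding of illness with period within a home comes from having two clusters, not from section 18.2. The planned independent variable is also measured light dose, so the shift above does not carry over directly.

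**Conclusion.** The point holds in a limited form. As written, other causes of a symptom are sought in SABL weeks and not in the weeks used as the reference, and after baseline no systematic illness record is kept alike in all periods. Attribution of side effects is therefore asymmetric. The documents do not allow the size of any resulting bias to be derived, and section 18.3 partly offsets it. For Aim 1, illness is unmeasured and could act in either direction; the CMAI figures above rest wholly on assumed illness share, score increment and SD. This is an inexpensive improvement that would make the protocol's own symptom comparison even-handed. It does not invalidate the planned analysis.

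**What to change.** - Add a short fixed list to the staff survey (procedure 3) at all seven visits in both homes: infection including urinary tract infection, delirium, fall, and new pain or painful procedure since the last visit.
- Apply the section 18.2 other-cause review to symptoms in control weeks on the same terms as in SABL weeks.
- Report symptom episodes by period: all episodes first, then split by whether another cause was found.
- Optionally, repeat the Aim 1 CMAI analysis without visits that had an acute event. This should remain a sensitivity analysis, because SABL could itself affect falls or delirium. It would not remove home-level confounding, and in a home-wide outbreak it would discard much of that home's data.

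The cost is a few more questions to the same informant at 40 × 7 = 280 planned resident-visits, so slightly longer interviews, plus extra review work in control weeks. That work may not be trivial, since every resident is enrolled with agitation and symptoms that trigger review will be common. No new staff or visits are needed.
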